- h) Hematology, blood chemistry, coagulation, and urinalysis can be performed within 24 hours (up to 72 hours if during weekend) prior to scheduled dosing. Screening results can be within 1 week prior to C1D1. Results must be obtained and reviewed prior to administration of RO7172508.
- i) Serology (as per local regulations) includes HIV, hepatitis B surface antigen, total hepatitis B core antibody, hepatitis C virus antibody. Results must be obtained and reviewed prior to administration of RO7172508.
- j) As part of the eligibility procedure, CEA expression will be confirmed on archival tumor material. A fresh tumor biopsy will be collected and assessed for eligibility ONLY if no archival tumor sample is available.
- k) Tumor response is assessed by the Investigator per RECIST v1.1 with the use of physical examination and image-based evaluation. All measurable and evaluable lesions should be assessed and documented during the screening period, within 7 days before Cycle 3 Day 1, thereafter every 6 weeks (± 7 days) for 12 weeks, and then every 12 weeks (± 7 days) until disease progression or death. (i.e. screening, C3, C5, C7, C11, C15, C19 etc.).
- l) All planned assessments are to be performed before administration of RO7172508. At least 24 hour (overnight) hospital stay required following the administration of study drug at Cycle 1 Day 1.
- m) sCEA sample to be taken on Cycle 2 only.
- n) Cytokines from Cycle 5 onwards, samples to be taken every second cycle up to Cycle 15 (e.g. C5, C7 etc.).
- o) Survival follow-up visit to be performed 90 days (± 7 Days) after the last treatment either in person or a phone call to document any ongoing or resolved AEs, and every 3 months (± 2 weeks) thereafter for overall survival.
- p) Sample to be taken only if a \geq Grade 2 safety event is suspected to be immune-related (e.g., IRR). Refer to [Table 5](#) for additional assessments if safety event is an IRR/CRS (\geq Grade 3) that requires tocilizumab treatment.
- q) sCEA sample at screening to be taken within 14 days of Cycle 1 Day 1.
- r) Samples required for Cycle 4 and Cycle 5 only.
- s) Vital signs include systolic and diastolic blood pressure; pulse rate; temperature; respiratory rate and oxygen saturation.
- t) Pulmonary function tests should include spirometry; forced expiratory volume (FEV1), forced vital capacity (FVC) and Diffusion capacity (DLCO).

Table 2 Part II: Multiple Participant Cohorts IV Q3W/Multiple Ascending Dose-Escalation

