- 12-lead ECG at screening (within one week before first dose of RO7172508). After Cycle 4, 12-lead ECG to be done only at every second cycle (i.e. Cycle 6, Cycle 8 etc.). Additional unscheduled ECG assessments in triplicate should be performed in case of abnormalities and if clinical symptoms occur. Recording must be done prior to PK sampling.

Table 2 Part II: Multiple Participant Cohorts IV Q3W/Multiple Ascending Dose-Escalation (cont.)

- e) Serum pregnancy test at screening, within 7 days prior to first dose, and at the safety follow-up visit; a urine pregnancy test will be performed at specified subsequent visits. If a urine pregnancy test is positive, it must be confirmed by a blood pregnancy test. Results must be obtained and reviewed prior to administration of RO7172508.
- f) Hematology, blood chemistry, coagulation, and urinalysis can be performed within 24 hours (up to 72 hours if during weekend) prior to scheduled dosing. Screening results can be within 1 week prior to C1D1. Results must be obtained and reviewed prior to administration of RO7172508.
- g) Tumor biopsy samples will be collected during screening, once during the study treatment period at Cycle 2 Day 8 and optionally at the end of treatment visit ONLY if the reason for discontinuation is progressive disease. If a fresh biopsy is performed for screening purposes, this can be used as the baseline sample.
- h) As part of the eligibility procedure, CEA expression will be confirmed on archival tumor material, *with the exception of CRC participants*. If no archival tumor sample is available, fresh sample will be collected and be assessed (the same sample would constitute as baseline screening sample if participant is enrolled). Archival tissue should be submitted for additional biomarker assessments for all participants (if available).
- i) Tumor response is assessed by the Investigator per RECIST V1.1 with the use of physical examination and image-based evaluation. All measurable and evaluable lesions should be assessed and documented during the screening period, within 7 days before Cycle 3 Day 1, thereafter every 6 weeks (± 7 days) for 12 weeks, and then every 12 weeks (± 7 days) until disease progression or death. (i.e. screening, C3, C5, C7, C11, C15, C19 etc.).
- j) All planned assessments are to be performed before administration of RO7172508. At least 24 hours (overnight) hospital stay required following administration of study drug at Cycle 1 Day 1.

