- y) Obinutuzumab ADA and PK samples to be taken only in Cycle 5 and 7 before administration of RO7172508.
- z) sCEA to be assessed for enrollment in cohorts with RO7172508 doses < 12 mg.
- aa) PD blood flow cytometry to be taken from Cycle 5 onwards only at Cycles 8,12 and 16 at predose

Table 3 Part II: Multiple Participant Cohorts SC QW/Multiple Ascending Dose-Escalation

Cycle (21 days)	Screening ^x	Cycle 1								Cycle 2 - 4 ^a				Cycle 5 onwards ^a				End of Treatment	Safety Follow-Up	Survival Follow-Up ^r	Unscheduled (Safety)
Day	D-28 to D-1	Day 1	Day 2	Day 3	Day 5 ^t	Day 8	Day 10 ^o	Day 15	Day 17	Day 1	Day 5 ^f	Day 8	Day 15	Day 1	Day 5 ^z	Day 8	Day 15				
Assessments ^a		pre-dose	24 hrs post dose (±2 hrs)	48 hrs post dose (±4 hrs)	96 hrs post dose (±5 hrs)	pre-dose	48 hrs post dose (±4 hrs)	pre-dose	48 hrs post dose (±4 hrs)	pre-dose	96 hrs post dose (±1 day)	pre-dose	pre-dose	pre-dose	96 hrs post dose (±5 hrs)	pre-dose	pre-dose	incl. early discont. visit (e.g. progressive disease)	60 days after last treatment	90 Days after last treatment then every 3 mths ^r	e.g. In the event of an IRR ≥G2 ⁿ
Informed Consent ^b	X																				
Eligibility	X																				
Demography	X																				
Medical History	X																				
Pulmonary Function Tests ^w	X																				
Archival Tissue ^h	X																				
Previous and Concomitant Treatments		X																			
Adverse Events		X																			
Physical Examination	X	X								X				X				X	X		X
Anthropometric Measurements ^q	X	X								X				X					X		
Vital Signs ^v	X	X	X	X	X	X	X	X	X	X	X	X	X	X	X	X	X	X	X	X	X
ECOG Performance Status	X	X								X				X				X	X		X
ECG-12 lead ^d	X	X			X					X	X			X ^d				X	X		
Pregnancy Test ^e	X									X				X					X		

Table 3 Part II: Multiple Participant Cohorts SC QW/Multiple Ascending Dose-Escalation (cont.)

Cycle (21 days)	Screening ^z	Cycle 1								Cycle 2 - 4 ^a				Cycle 5 onwards ^a				End of Treatment	Safety Follow-Up	Survival Follow-Up ^r	Unscheduled (Safety)
Day	D-28 to D-1	Day 1	Day 2	Day 3	Day 5 ^t	Day 8	Day 10 ^o	Day 15	Day 17	Day 1	Day 5 ^r	Day 8	Day 15	Day 1	Day 5 ^{c,t}	Day 8	Day 15				

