- s) All planned assessments are to be performed before administration of RO7172508.
- t) Day 5 visit optional if it falls on a non-working day *and can be performed +/- 1 day.*
- u) Serology (as per local regulations) includes HIV, hepatitis B surface antigen, total hepatitis B core antibody, hepatitis C virus antibody. Results must be obtained and reviewed prior to administration of RO7172508.
- v) Vital signs include systolic and diastolic blood pressure; pulse rate; temperature; respiratory rate and oxygen saturation.

Table 3 Part II: Multiple Participant Cohorts QW SC/Multiple Ascending Dose-Escalation (cont.)

- w) Pulmonary function tests should include spirometry; forced expiratory volume (FEV1), forced vital capacity (FVC) and Diffusion capacity (DLCO).
- x) Refer to [Table 6](#) in the event obinutuzumab pre-treatment is implemented for specific additional assessments during the screening period.
- y) Obinutuzumab ADA and PK samples to be taken only in Cycle 5 and 7 before administration of RO7172508.
- z) sCEA to be assessed for enrollment in cohorts with RO7172508 doses < 12 mg.
- aa) PD blood flow cytometry to be taken from Cycle 5 onwards only at Cycles 8,12 and 16 at predose

Table 4 Part II: Fractionated Dosing IV Cohort for Q3W

Cycle (21 days)	Screening ^v	Cycle 1											Cycle 2 - 4 ^a				Cycle 5 onwards ^a			End of Treatment	Safety Follow-Up	Survival Follow-Up ^r	Un-scheduled (Safety)			
Day	D-28 to D-1	Day 1		Day 2	Day 3	Day 8	Day 9 ^p	Day 15	Day 16 ^p	Day 1	Day 3	Day 8	Day 15	Day 1	Day 3 ^c	Day 15										
Assessments ^a		pre-dose	EOI +15 mins	2 hrs EOI ±15 mins	24 hrs EOI ±2 hrs	48 hrs EOI ±4 hrs	pre-dose	EOI +15 mins	24 hrs EOI ±2 hrs	pre-dose	EOI +15 mins	24 hrs EOI ±2 hrs	pre-dose	EOI +15 mins	2 hrs EOI ±15 mins	48 hrs EOI ±4 hrs			pre-dose	EOI +15 mins	48 hrs EOI ±4 hrs	incl. early discontin. visit (e.g. progressive disease)	60 Days after last treatment (±5 Days)	90 Days after last treatment then every 3 mths ^r	e.g. In the event of an IRR ≥G2 ^o	
Informed Consent ^b	X																									
Eligibility	X																									
Demography	X																									
Medical History	X																									
Pulmonary Function Tests ^v	X																									
Archival Tissue ^h	X																									
Previous and Concomitant Treatments		X																								
Adverse Events		X																								
Physical Examination	X	X											X						X				X	X		X

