Symptoms of IRRs and CRS, during or after infusion of RO7172508, may be indistinguishable from each other and might be life-threatening. CRS is a disorder characterized by nausea, headache, tachycardia, hypotension, rash, dyspnea, and renal, coagulation, hepatic and neurologic disorders; CRS is caused by the release of cytokines from cells (Lee et al 2014). Severe CRS may be associated with other clinical sequelae such as disseminated intravascular coagulation and capillary leak syndrome. Standard of care for severe or life threatening CRS resulting from immune-based therapy has not been established, especially in solid tumors.

In case of IRR/CRS, the recommended management is detailed in [Table 17](#).

The activity of RO7172508 at the tumor site leads to the destruction of the tumor cells and tumor inflammation/flare. Given this mechanism of action, AEs associated with tumor inflammation are expected. These AEs are expected to occur shortly following RO7172508 administration and can affect organ systems with the location of the tumor lesions. These events might be life-threatening especially in case of critical location of the tumor (respiratory tract) or extensive tumor size.

Because of a higher affinity to CEA of RO7172508 compared to *cibisatamab*, the severity of adverse reactions may be higher; however, the difference in the potency has been taken into account in the evaluation of the starting-dose proposed in this study. Stringent risk mitigation measures, including required appropriate organ function at baseline (cardiac, pulmonary, liver, hematologic function), close monitoring of participants, especially around the first infusion (including 24-hour hospitalization after the first infusion), staggered enrollment, dose-escalation rules and detailed instructions regarding management of specific AEs are designed to minimize risks. Overall, these potential risks are considered manageable and acceptable in the context of anticipated benefit.

Risk mitigation has been considered in the study design and management of potential AEs is described in *Section 8.3.8 of the protocol* and the [RO7172508 Investigator's Brochure](#).

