Once the IV schedule has shown RO7172508 preliminary clinical activity, defined by partial response (PR) or better, according to RECIST v. 1.1 (Appendix 6), or the MTD has been established and is equal to or above 2 mg, the SC multiple-ascending dose-finding cohorts could be initiated. The starting-dose and regimen (QW or Q3W) for SC administration will be proposed based on the evaluation of the safety and PK data observed following IV administration but will not exceed the highest safe dose tested in the IV Q3W dose escalation; however, due to practical considerations, a minimum dose of 2 mg is defined for a single SC administration. In addition, the QW SC starting-dose will not exceed one third of the IV MTD or of the highest safe IV dose tested.

Dose escalation in the SC treatment group will proceed until the SC MTD/OBD has been determined (see Section 4.1.2). *If the SC treatment group is started Q3W at a dose <6*

mg, the QW schedule can be evaluated once the dose is ≥ 6 mg. Data from this treatment group will establish if the SC route of administration, which will have a lower C_{max} than IV after first administration, can show comparable efficacy and/or comparable or improved safety profile of a TCB either QW and/or Q3W.

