6.1.1 Pre-medication

All pre-medications should be captured as concomitant medications in the participant's electronic Case Report Form (eCRF). If during dose-escalation Grade ≥ 2 IRRs/CRS or tumor inflammatory events occur in the majority of participants, the utility of prophylactic pre-medication with systemic corticosteroids in preventing such events may be tested using the regimen as outlined in [Table 14](#) (flat dosing) and [Table 15](#) (for fractionated dosing). If successful, this regimen will then be used in future cohorts.

In the event that the change in the route of administration from IV to SC does not mitigate the tumor inflammatory events or IRRs, then the same steroid regimen may be implemented as described in [Table 14](#) and [Table 15](#). These regimens are based on the expected duration of inflammatory events and they may be reduced or modified based on emerging data. *Also, they may be extended from Cycle 1 to subsequent cycles, in case tumor inflammation and/or IRR occur at later cycles.* Pre-medication may also include 1000 ml saline, 50 mg indomethacin (or equivalent non-steroidal anti-inflammatory [NSAID]), and 50 mg diphenhydramine (or equivalent H1 antagonist).

Table 14 Steroid Use on Cycle 1 of RO7172508 Infusion to be implemented in the event of frequent IRR/CRS or gastrointestinal RO7172508-related toxicity occurrence after first administration

Timing	Dose
C1D1: 4 to 6 hours before RO7172508 infusion	1 mg/kg methylprednisolone IV* 1 g paracetamol PO TID 2 mg loperamide PO
C1D1: approximately 2 hours after RO7172508 infusion	1 mg/kg methylprednisolone IV*
C1D2: approximately 24 hours post-RO7172508 EOI	1 mg/kg prednisone IV/PO* 1 g paracetamol PO TID 2 mg loperamide PO**
C1D3: approximately 48 hours post-RO7172508 EOI	0.5 mg/kg prednisone IV/PO* 1 g paracetamol PO TID
C1D4: approximately 72 hours post-RO7172508 EOI	0.5 mg/kg prednisone IV/PO* 1 g paracetamol PO TID

C: Cycle; D: Day; EOI: end of infusion; IV: intravenous; PO: oral; TID: 3 times a day.

* rounded up to next multiple of 10 mg (or equivalent doses of mid acting steroids)

** subsequent treatment with loperamide only to be given as clinically indicated

Table 15 Steroid Use on Cycle 1 of RO7172508 or gastrointestinal RO7172508-related toxicity to be implemented in the event of frequent IRR/CRS persisting despite dose fractionation

Timing	Dose

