8.3.8.1 Infusion-Related Reactions/Cytokine Release Syndrome

Administration of RO7172508 may cause a spectrum of infusion-related adverse events that typically occur during, shortly after, or within 24 hours after the infusion and could be associated with an IRR or CRS.

IRRs are typically seen with the first two cycles and without symptoms of hypoxia and/or hypotension. In contrast, CRS is more likely to occur with the symptoms of hypoxia and/or hypotension at any cycle and with any symptom following from the third cycle onward. IRR events are therefore defined as taking place in association with the first two infusions and without symptoms of hypotension and/or hypoxia.

Given the overlap in signs and symptoms, IRRs may be indistinguishable from CRS, defined as a disorder characterized by nausea, headache, tachycardia, hypotension, rash, shortness of breath, and renal, coagulation, hepatic, and neurologic disorders ([Lee et al. 2014](#)). Severe CRS may be associated with other clinical sequelae, such as disseminated intravascular coagulation and capillary leak syndrome.

Given that IRRs may be indistinguishable from CRS based on symptomatology, single-treatment management guidelines are being recommended for both IRRs and CRS, during or up to 24 hours after infusion of RO7172508. The approach to have single-treatment management guidelines for IRR and CRS will continue to be reviewed as additional safety data accumulate.

[Table 17](#) provides guidelines for management of infusion-related reactions/ cytokine release syndrome.

Table 17 Recommendations for Management of IRRs and CRS considered related to RO7172508^a

Symptoms	Guidance

Grade 1 Fever, constitutional symptoms
	
 – If RO7172508 infusion is ongoing, slow infusion to ≤50% or interrupt infusion – Symptomatic treatment and supportive care – Monitor fluid balance and administer IV fluids as clinically indicated – At next cycle administer pre-medications that may include antihistamine, antipyretics/NSAIDs, antiemetic, and corticosteroids (See Table 14 and Table 15)

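### The SC weekly schedule (Table 3) omits the 24-hour hospital stay after the first dose that the other four RO7172508 schedules require, and has no timed check before the 24 h visit

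*Combined protocol and SAP*

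**What the plan says.** Five tables in Section 1.3 schedule RO7172508 dosing: Table 1 (Part I IV), Table 2 (Part II IV Q3W), Table 3 (SC QW), Table 4 (fractionated IV) and Table 7 (SC Q3W). Tables 5 and 6 cover tocilizumab use and obinutuzumab screening.

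- Table 1 footnote l: "At least 24 hour (overnight) hospital stay required following the administration of study drug at Cycle 1 Day 1".
- Tables 2, 4 and 7, footnote j in each: "At least 24 hours (overnight) hospital stay required following administration of study drug at Cycle 1 Day 1".
- Table 3 footnote s: "s) All planned assessments are to be performed before administration of RO7172508". It ends there, and no other Table 3 footnote mentions a stay.

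In Table 3, Cycle 1 Day 1 has a pre-dose column only. The next timed column is Day 2, "24 hrs post dose (±2 hrs").

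Section 2.3 counts the stay among the measures that make the risk acceptable: "close monitoring of participants, especially around the first infusion (including 24-hour hospitalization after the first infusion"). Section 8.3.8.1 says that infusion-related events "typically occur during, shortly after, or within 24 hours after the infusion". Section 6.1.1 plans steroid prophylaxis "In the event that the change in the route of administration from IV to SC does not mitigate the tumor inflammatory events or IRRs". Section 4.1 states that "a minimum dose of 2 mg is defined for a single SC administration".

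**The concern.** A site that follows Table 3 exactly may discharge a participant on the day of a first dose of a T-cell bispecific, with nothing timed until the next day. That is the period in which the protocol expects infusion-related reactions (IRR) and cytokine release syndrome (CRS), which Section 2.3 describes as possibly life-threatening. Section 2.2.1 adds that no in vivo toxicity studies were done. The protocol does not assume that SC dosing removes the risk, since Section 6.1.1 provides for the case where it does not. What is at stake is required observation of the participant just dosed. A lesser effect is that onset of symptomatic events is recorded less precisely. This has some bearing on dose-limiting toxicities, because the Grade 3 tumor pain and hypoxia exceptions in Section 4.1.3.1 depend on onset within 24 hours.

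**Working it through.** The plan has no figure to reproduce here. The check compares the schedules and then tests whether anything in the protocol explains the difference.

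**Step 1. Cycle 1 Day 1 safeguards by schedule (Section 1.3)**

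| Schedule | 24 h stay | Timed post-dose checks before 24 h |
|---|---|---|
| Table 1, Part I IV | Yes (l) | 2 (end of infusion, 2 h) |
| Table 2, IV Q3W | Yes (j) | 2 (end of infusion, 2 h) |
| Table 4, fractionated IV | Yes (j) | 2 (end of infusion, 2 h) |
| Table 7, SC Q3W | Yes (j) | 0 |
| Table 3, SC QW | **No** | **0** |

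The stay is required in 4 of 5 schedules. Table 3 is the only one with neither safeguard.

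**Step 2. Time to the first required post-dose check in SC QW**

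Earliest: 24 h − 2 h = 22 h. Latest: 24 h + 2 h = 26 h. That span covers most or all of the 24-hour window in Section 8.3.8.1.

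**Step 3. Could a feature of SC QW explain the exemption?**

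- *Route.* Section 4.1 expects a lower C<sub>max</sub> with SC than with IV after the first administration. That applies equally to SC Q3W, which keeps the stay.
- *Smaller first dose.* The QW starting dose is capped at one third of the IV MTD or of the highest safe IV dose. Small first doses keep the stay elsewhere. Fractionated IV starts at 10% of the planned dose (Section 4.1), a smaller fraction than one third. Part I starts at 65 µg, and the 2 mg SC minimum is 2000 / 65 ≈ 31 times that. It also exceeds the Part I maximum of 1.6 mg.
- *Duration of the cap.* It binds the QW starting dose only. Section 4.1.2.2 lets QW escalate to 160 mg, and Table 3 footnote s would still require no stay at a participant's first dose.
- *Same dose, different rule.* The 2 mg minimum applies to any single SC dose, so a first SC dose of 2 mg can require a stay under Q3W and none under QW.

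**Step 4. Does other text supply the stay?**

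Only Section 2.3 comes near, and it speaks of the first infusion. If that word includes SC injection, Table 3 fails to carry out a stated safeguard. If it does not, no text covers SC QW. Both readings lead to the same edit.

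**The case against.** The strongest counter-argument is that the exemption may be deliberate. SC Q3W may start at the highest safe IV dose, whereas QW may not exceed one third of the IV MTD or highest safe dose. A 2 mg QW start therefore implies at least 3 × 2 = 6 mg tolerated IV, while 2 mg Q3W could be at the IV MTD itself. Equal milligrams do not mean equal relative risk. That is fair as far as it goes, but the protocol does not offer it as the reason, the cap does not limit later QW cohorts, and regimens with proportionally smaller first doses keep the stay.

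Several other points stand as qualifications:

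- SC cohorts open only after IV activity or an established IV MTD or OBD, and the one-week gap between the first and second participant in a cohort applies. This limits how many participants are exposed at once, but does not observe the one just dosed.
- Adverse events are recorded continuously and an unscheduled safety visit exists. The gap is in required, timed observation, not in reporting.
- The lack of an early timed check is shared with Table 7. It matters in Table 3 because no stay covers it.
- The protocol uses the word infusion loosely; the SC table itself speaks of weight recorded before infusion. Section 2.3 may well have been meant to cover SC, in which case Table 3 simply does not carry it through.
- The effect on event timing is minor, and the conclusion does not depend on it.

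**Conclusion.** The concern holds. SC QW is the one schedule of five without the 24-hour stay, and the only one with neither a stay nor a timed check before the 24 h visit. The first required post-dose observation comes 22 to 26 hours after the first dose. The documents give no reason, and the explanations that can be drawn from them (route, peak concentration, starting-dose cap) do not separate SC QW from regimens that keep the stay.

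The conclusion rests on the wording of the schedules and on the protocol's own risk window for IRR and CRS. It does not depend on any assumed event rate. Whether the omission is an oversight or a choice cannot be settled from the documents. It is an inexpensive safety correction that should be made, and it does not affect the analysis or the sample size.

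**What to change.** Add to Table 3 footnote s the sentence already used in Table 7 footnote j: "At least 24 hours (overnight) hospital stay required following administration of study drug at Cycle 1 Day 1". In Section 2.3, word the hospitalization measure for the first administration rather than the first infusion, so that it covers both routes. The stay closes the gap left by the missing early check in the same way that it does in Table 7.

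The cost is two wording edits and one overnight stay per SC QW participant, which every other schedule already imposes. If the sponsor intends to exempt SC QW, the protocol should say so, give the reason, and state what observation applies in the first 24 hours instead.
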